3.6.10 Personal Health Questionnaire Depression Scale-8

The PHQ-8 assesses symptoms of depression over the last 2 weeks by asking eight questions related to depression (see Appendix R in the clinical study protocol for more details).

The mean change from baseline in PHQ-8 total score will be assessed by visit up to Week 52 as well as at Week 60. The PHQ-8 total score will be derived as the sum of the 8 single item scores, each ranging from 0 (not at all) to 3 (nearly every day). If more than one item is missing, then the value of the scale is set to missing.

3.7 Pharmacokinetics, pharmacodynamics, and immunogenicity

3.7.1 Immunogenicity variables

Anti-drug antibodies (ADA) assessments will be conducted utilising a tiered approach (screen, confirm, titre).

The proportion of subjects with ADA responses during the treatment and follow-up periods will be summarised. Anti-drug antibody response categories summarised will include (but are not limited to):

- ADA prevalence: a positive ADA result at any visit including study baseline and all post-baseline measurements
- ADA negative: does not meet criteria for ADA positive
- Subjects who are ADA positive at baseline only
- Subjects who are ADA positive post-baseline only
- Subjects who are ADA positive at both baseline and post-baseline
- Subjects who are ADA positive by visit
- Subjects who are ADA positive at a post-baseline measurement for the first time (for subjects who are ADA negative at baseline) by visit
- ADA persistently (4 months) positive: positive at ≥ 2 post-baseline assessments, with ≥ 16 weeks between first and last positive or positive at last post-baseline assessment (for subjects who are ADA negative at baseline)
- ADA prolonged (6 months) persistently positive: positive at ≥ 2 post-baseline assessments, with ≥ 24 weeks between first and last positive or positive at last post-baseline assessment (for subjects who are ADA negative at baseline)
- ADA prolonged (12 months) persistently positive: positive at ≥ 2 post-baseline assessments, with ≥ 48 weeks between first and last positive or positive at last post-baseline assessment (for subjects who are ADA negative at baseline)
- ADA transiently (<4 months) positive: at least 1 post-baseline ADA positive assessment and not fulfilling the conditions of ADA persistently positive (for subjects who are ADA negative at baseline)

- ADA positive with titre \leq median of maximum titre. To calculate the median of maximum titre, take the maximum value for each subject, then calculate the median of these values across all subjects (for subjects who are ADA negative at baseline and ≥ 1 post-baseline ADA result available).
- ADA positive with titre $>$ median of maximum titre (for subjects who are ADA negative at baseline and ≥ 1 post-baseline ADA result available).
- Neutralising antibody (nAb) incidence: post-baseline nAb positive result only (not positive at baseline)
- Prolonged (6 months) nAb positive: nAb positive at ≥ 2 post-baseline assessments, with ≥ 24 weeks between the first and last positive or positive at last post-baseline assessment (for subjects who are nAb negative at baseline).
- Prolonged (12 months) nAb positive: nAb positive at ≥ 2 post-baseline assessments, with ≥ 48 weeks between the first and last positive or positive at last post-baseline assessment (for subjects who are nAb negative at baseline).

For the presentation of ADA results at a single time point (e.g. baseline or by visit summaries), the corresponding titre summary will be based on the titres of the positive samples for that particular visit. For the presentation of ADA results across visits (e.g. any post-baseline), the corresponding titre summaries will be based on the maximum titre of all positive samples for each subject. Titres of positive measurements reported as ≤ 30 (minimum required dilution) will be imputed as 30.

The presence of nAb will be tested in all ADA-positive samples using a ligand binding assay. The following variables will be evaluated:

- Proportion of subjects with at least one non-missing ADA result (at any time) who are nAb positive at any time
- Proportion of subjects with at least one non-missing ADA result (at any time) who are nAb positive for the first time by visit
- Proportion of subjects with a non-missing ADA result (at a specific visit) who are nAb positive by visit

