4.2.2 Follow-up visits after premature discontinuation of investigational product

Subjects who agree to continue scheduled visits until Week 52 (if IP discontinued prior to Week 52) or Week 104 (if IP discontinued after Week 52):

Subjects who prematurely discontinue IP (see [Section 3.9](#)) should have a 24-hour UPCR measurement within 4 weeks of the decision to discontinue IP and before the start of a new treatment for LN.

Subjects who discontinue IP will be asked to return for all regular clinic visits. All study assessments will be performed if possible; however, at a minimum, the following assessments should be completed:

- Lupus Serology tests (anti-dsDNA antibodies, C3, C4)
- PGA (Physician's Global Assessment)

- 24-hour urine for protein, creatinine and spot UPCR

The following safety assessments should also be completed:

- Serum chemistry, haematology, urinalysis
- Vital signs
- Physical examination, weight
- Adverse events including AESIs
- TB Questionnaire
- Concomitant medications

Subjects who are unwilling to continue to Week 52 or Week 104:

If during the 52 week double-blind treatment period, the subject is unwilling to continue through Week 52, he/she should complete Week 52 visit and be followed for 12 weeks after the last administration of IP by completing the Follow-up Visits, unless consent is withdrawn. If during the second year extension period, the subject is unwilling to continue through Week 104, he/she should complete Week 104 visit and be followed for 12 weeks after the last administration of IP by completing the Follow-up Visits, unless consent is withdrawn.

If the subject does not agree to return for any clinic visits and perform the laboratory testing requirements of these visits, he/she will be asked if he/she can be followed on a monthly basis via telephone calls for 12 weeks after last dose of IP administration. At these calls, he/she will be asked about AEs/SAEs, lupus symptoms, and lupus medications. Steroid bursts will also be captured.

Subjects who withdraw consent:

If the subject indicates his/her intention to withdraw consent, attempts should be made to complete the Week 52/discontinuation or Week 104/discontinuation visit as applicable before the consent is withdrawn. However, no study procedures or data collection can occur after the subject withdraws consent.

Adverse events will be followed up per Section [6.5.2](#).

4.3 **Unscheduled visit**

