4.2.7.1 Analysis methods for immunogenicity variables

The proportion of subjects with ADA results as described in Section 3.7.1 will be presented together with descriptive statistics of the available titres. Descriptive statistics will include n (number of reportable titres), minimum, quartiles (1st quartile, median and 3rd quartile) and maximum.

ADA response and the corresponding titre will be summarised at baseline and at all scheduled post-baseline visits in the study period by treatment group for the full analysis set. In addition, the proportion of ADA positive subjects will be presented cumulatively.

A summary of key subject information will be provided for ADA positive subjects.

The analyses of impact of ADA on PK and PD endpoints are described in Sections 4.2.7.2 and 4.2.7.3.

Pre-specified AE categories and hypersensitivity events during the on-treatment period will be summarised by ADA status (positive, negative).

Additional summaries of immunogenicity data may be generated based on the results of the above analyses.

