4.3 Subgroup analysis

To explore the uniformity of the detected overall treatment effect, subgroup analyses will be performed for the following factors:

- Type I IFN 4-gene test at screening (IFN test-high, IFN test-low)
- 24-hour UPCr at screening ≤ 3 mg/mg, >3 mg/mg
- Age (≥ 18 to 64, ≥ 65 years)
- Placebo response region (low placebo response rate versus high placebo response rate)
Countries with a low placebo response rate versus high placebo response rate are defined as [Low: Australia, Belgium, France, Germany, Italy, South Africa, Spain, United Kingdom, United States], [High: Argentina, Hungary, Republic of Korea, Mexico, Peru, Poland, Russian Federation, Serbia, Taiwan]
- Race (white; black or African American; Asian, native Hawaiian or other Pacific Islander; American Indian or Alaska native; other)
- Screening biopsy classification (class III, class IV, mixed [class III or IV + class V])
- Number of methylprednisolone pulses (1, >1). Pulses are counted during the whole study.
- ADA result (Positive at any time, Negative)
- OCS at baseline (<20 mg/day, ≥ 20 mg/day)
- eGFR at baseline (<60 mL/min/1.73m², ≥ 60 mL/min/1.73m²)

Table 3, Table 4 and Table 5 give an overview of subgroup analyses to be performed at Week 24, 52 and Week 104, respectively. Where necessary (e.g. for subgroup analysis based on stratification factors), the model factors will be reduced. If not stated otherwise, the subgroup analysis will not be performed for a sub-population if any treatment group consists of less than 10 subjects within that sub-population. Where a sub-population contains less than 10 subjects in any treatment group, only ns and treatment estimates will be presented (no treatment comparisons will be presented).

Forest plots will be used to summarise the estimates of the treatment effect for the applicable subgroups.

Table 3 Overview of subgroup analyses at Week 24

Analysis	IFN test	24-hour UPCR	OCS at baseline
24-hour UPCR	X	X	X
CRR	X	X	X

Table 4 Overview of subgroup analyses at Week 52

Analysis	IFN test	24-hour UPCR	Age	Placebo response	Race	Number of methylprednisolone pulses	Screening biopsy	ADA result	OCS at baseline	eGFR at baseline
24-hour UPCR	X	X	X	X	X	X	X	X	X	X
CRR	X	X	X	X	X	X	X		X	X
aCRR	X	X							X	
PRR	X	X				X	X			
Graded CRR	X	X				X	X			
OCS tapering	X	X		X		X	X			

Table 5 Overview of subgroup analyses at Week 104

Analysis	IFN test	24-hour UPCR	OCS at baseline	eGFR at baseline
24-hour UPCR	X	X	X	X
CRR	X	X	X	X

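### SAP 3.7.1 reports a treated subject with no positive result and no post-dose ADA sample as ADA negative; such subjects should be shown as not evaluable

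*SAP*

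**What the plan says.** SAP 3.7.1 counts a subject as positive on any one positive sample, baseline included: "ADA prevalence: a positive ADA result at any visit including study baseline and all post-baseline measurements". The negative category is the complement: "ADA negative: does not meet criteria for ADA positive". No sample is required for it.

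Two other items in the same section do carry a condition. The titre categories are limited to subjects "ADA negative at baseline and ≥ 1 post-baseline ADA result available", and the neutralising-antibody measure is the "Proportion of subjects with at least one non-missing ADA result (at any time) who are nAb positive at any time".

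SAP 4.2.7 places immunogenicity analyses on the full analysis set. SAP 2.1.2 defines that set by randomisation and at least one dose, and SAP 4.1.3 makes the whole set the default denominator for percentages. No ADA-evaluable set is defined. On reactions, SAP 4.2.7.1 says: "Pre-specified AE categories and hypersensitivity events during the on-treatment period will be summarised by ADA status (positive, negative". SAP 4.2.6.1 adds an adverse-event summary by ADA category, and SAP 4.2.7.2 and 4.2.7.3 split PK and PD summaries by ADA status. None of these names a column for unknown status.

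Protocol Table 2 schedules ADA before dosing at Week 0 and then at Weeks 12, 24, 36 and 52 or early discontinuation. Protocol Table 3 adds samples 8 and 12 weeks after the final dose. For subjects who stop investigational product, Protocol 4.2.2 asks for all assessments where possible but sets a floor: "at a minimum, the following assessments should be completed". ADA is not on the list that follows.

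**The concern.** A missing result is treated as a negative one. The first scheduled post-dose sample is drawn at Week 12, after the infusions at Weeks 0, 4 and 8. A subject who stops during that time and gives no later sample has at most a pre-dose result, which says nothing about antibodies induced by treatment.

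The tables by ADA status are meant to show whether antibody formation goes with hypersensitivity or other events. Events in unsampled subjects are credited to the negative column as if an antibody had been looked for and not found. ADA-positive subjects may be few, so a few misplaced subjects can matter to the descriptive comparison even when they barely change the ADA-positive proportion.

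**Working it through.** The plan states no figure to reproduce. The check traces the definition through the plan and then illustrates the size with assumed counts.

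**Step 1: classification.** Take a subject who received one dose, has a negative or missing baseline ADA result and has no post-dose result. The subject is in the full analysis set, does not meet the positive criterion, and so is ADA negative. A subject positive at baseline with no later sample is ADA positive and is not affected.

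**Step 2: who can reach this state.** Stopping product is not enough. Protocol 3.9.9 and Table 2 footnote b keep such subjects on the visit schedule and require a discontinuation visit if they then leave. The Week 52/discontinuation column includes ADA, and so do both follow-up visits. To remain unsampled, a subject must miss all of these, for example through telephone-only follow-up, attendance for the minimum set only, or withdrawal of consent without a discontinuation visit (Protocol 4.2.2).

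**Step 3: size for hypersensitivity.** Assumptions: N = 100 anifrolumab subjects (two thirds of 150), p = 5 ADA positive, h = 3 hypersensitivity subjects among sampled negatives, u unsampled subjects, a of them reactors.

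- Negative column as planned: (h + a) / (N − p)
- Sampled negatives only: h / (N − p − u)

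| u | a | As planned | Sampled negatives only |
|---|---|---|---|
| 2 | 0 | 3/95 = 3.2% | 3/93 = 3.2% |
| 2 | 1 | 4/95 = 4.2% | 3/93 = 3.2% |
| 5 | 2 | 5/95 = 5.3% | 3/90 = 3.3% |
| 10 | 0 | 3/95 = 3.2% | 3/85 = 3.5% |
| 10 | 5 | 8/95 = 8.4% | 3/85 = 3.5% |

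The planned column is too high when a/u exceeds the rate in sampled negatives, and too low when it is below.

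**Step 4: size for the ADA-positive proportion.** With 5 positives, 5/100 = 5.0% becomes 5/98 = 5.1%, 5/95 = 5.3% or 5/90 = 5.6% for u = 2, 5 or 10. With 10 positives, 10.0% becomes 10.2%, 10.5% or 11.1%. This effect is small.

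**Step 5: size for a commoner event.** Assume 4 positives, 91 sampled negatives with event rate r, and 5 unsampled subjects of whom 3 have the event. The shift in the negative column is (91r + 3)/96 − r = (3 − 5r)/96. That is 3/96 = 3.1 points at r = 0, (3 − 1.2)/96 = 1.9 points at r = 24%, and zero at r = 60%.

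**The case against.** The strongest reply is that the sampling plan leaves few such subjects. There are several planned post-dose samples after an early stop, and the minimum set is a fallback. A reader might infer that anyone who stops for a reaction is counted as negative untested; the documents do not support that. This part of the objection stands and limits the point to subjects who give no later sample at all.

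The direction of bias is also open. A reader might infer that event rates in the negative column are inflated. That holds only if unsampled subjects left mainly because of such events. Treatment-period adverse events run to 28 days after the last dose (SAP 3.6.1), so someone who leaves early for another reason has little time at risk and can lower the rate.

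A reader might also infer that the comparison by ADA status could be reversed. On the Step 5 counts, a strict reversal needs k/4 to lie between x/91 and (x + 3)/96, where k and x are the events in positives and sampled negatives. Only k = 1, x = 22 does this: 25.0% against 22/91 = 24.2%, which becomes 25/96 = 26.0%. With 4 positives each event is worth 25 points, so that comparison says little however unsampled subjects are handled.

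Nor does the efficacy subgroup in SAP 4.3 suffer materially. ADA result is marked only for 24-hour UPCR at Week 52. That variable is first measured after baseline at Week 12, and SAP 4.2.1 drops data after the last infusion. Someone who stops before Week 12 therefore contributes no post-baseline value. Treatment comparisons are also withheld where any treatment group has fewer than 10 subjects in the sub-population.

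The contrast within SAP 3.7.1 is only moderate evidence of an oversight. The titre condition serves a median calculation, and the neutralising-antibody condition is met by a baseline sample alone. The category list is open-ended and further summaries are allowed, but adding categories does not change who is called negative.

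**Conclusion.** The misclassification follows from the plan's own definition, analysis set and two-column tables, and does not depend on any assumed number. Its size does. The number of treated subjects with no positive and no post-dose result is not given and is probably small. With 2 to 10 such subjects among 100, the ADA-positive proportion changes by about 0.1 to 1.1 points. The hypersensitivity rate in the negative column changes by anything from about −0.4 points (3.2% against 3.5%) to +4.9 points (8.4% against 3.5%) in the cases tabulated. The direction depends on why the subjects left.

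The effect is confined to descriptive immunogenicity, adverse-event, PK and PD summaries. The primary and secondary tests are untouched, and the 24-hour UPCR subgroup is not materially changed. This is a clarification worth making before unblinding, not a threat to the trial's conclusions.

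**What to change.** In SAP 3.7.1:

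- leave ADA positive as it is: a positive result at any visit, baseline included;
- define ADA negative as at least one post-baseline ADA result and no positive result at any visit;
- define 'not evaluable' as no positive result and no post-baseline result.

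Show the 'not evaluable' subjects, with their events, as a separate column in the ADA, adverse-event and hypersensitivity tables, and state the denominator for each percentage. Use the same definitions wherever ADA status is used elsewhere. Keeping the positive definition unchanged matters: a rule that made every subject without a post-baseline sample 'not evaluable' would remove baseline-positive subjects whom the SAP counts as positive.

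The cost is a short addition to the SAP, one extra table column and slightly smaller denominators. No new sampling is needed.

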3.7.2 Pharmacokinetic variables

PK samples will be collected both pre and post-dose for specific infusions of investigational treatment. Due to the limited sampling schedule, the PK assessment for both anifrolumab and mycophenolate will be primarily based on the observed steady-state serum trough (pre-dose) concentrations, C_{trough} . For anifrolumab, maximum concentrations after the first and last dose of the first year will also be evaluated.

Individual concentrations will be reviewed for exclusion from descriptive statistics by identifying outliers and reviewing dosing information and sample collection times. Analysis to determine if the identified concentrations should be excluded includes visual inspection of PK-time profiles and comparison of descriptive stats with identified concentrations excluded and included.

In the second year extension period, only C_{trough} will be assessed.

3.7.3 Pharmacodynamic outcome variables

The IFN21 gene PD signature is calculated as the mean expression level of 21 IFN-inducible genes in lupus nephritis subjects compared to the expression level in control samples from healthy individuals. The IFN21 gene PD signature following treatment is compared to the IFN21 signature at baseline for each subject at multiple timepoints after treatment. The “percent suppression of fold change” will be presented as the “percent of baseline IFN21 PD signature” in all summaries, figures and listings.

This variable will be derived as defined in [Appendix H](#).

3.7.4 Lupus Serology variables

The outcome variable for anti-dsDNA, C3 and C4 complement levels will be the mean change from baseline longitudinally up to Week 104 in subjects with abnormal complement level at baseline, defined as complement level below lower limit of normal, or elevated anti-dsDNA at baseline.

Elevated anti-dsDNA is defined as an anti-dsDNA value above the lower limit for a positive value.

4 ANALYSIS METHODS

4.1 General principles

4.1.1 Visit windows

For visit based analyses, the variables will be summarised based on the scheduled days with adjusted analysis-defined visit windows. The adjusted analysis-defined windows are summarised below:

Table 2 Visit windows

Adjusted Defined Windows Visit	Scheduled Study Day	Maximum Windows
Day 1	1	Study Day 1
Week 4	29	$2 \leq \text{Study Day} \leq 42$
Week 8	57	$43 \leq \text{Study Day} \leq 70$
Week 12	85	$71 \leq \text{Study Day} \leq 98$
Week 16	113	$99 \leq \text{Study Day} \leq 126$
Week 20	141	$127 \leq \text{Study Day} \leq 154$
Week 24	169	$155 \leq \text{Study Day} \leq 182$
Week 28	197	$183 \leq \text{Study Day} \leq 210$

Adjusted Defined Windows Visit	Scheduled Study Day	Maximum Windows
Week 32	225	211 ≤ Study Day ≤ 238
Week 36	253	239 ≤ Study Day ≤ 266
Week 40	281	267 ≤ Study Day ≤ 294
Week 44	309	295 ≤ Study Day ≤ 322
Week 48	337	323 ≤ Study Day ≤ 350
Week 52	365	351 ≤ Study Day ≤ 378
Week 56	393	379 ≤ Study Day ≤ 406
Week 60	421	407 ≤ Study Day ≤ 434
Week 64	449	435 ≤ Study Day ≤ 462
Week 68	477	463 ≤ Study Day ≤ 490
Week 72	505	491 ≤ Study Day ≤ 518
Week 76	533	519 ≤ Study Day ≤ 546
Week 80	561	547 ≤ Study Day ≤ 574
Week 84	589	575 ≤ Study Day ≤ 602
Week 88	617	603 ≤ Study Day ≤ 630
Week 92	645	631 ≤ Study Day ≤ 658
Week 96	673	659 ≤ Study Day ≤ 686
Week 100	701	687 ≤ Study Day ≤ 714
Week 104	729	715 ≤ Study Day ≤ 742
Week 108	756	743 ≤ Study Day ≤ 770
Week 112	784	771 ≤ Study Day ≤ 798

For assignment of data to time points using the visit windows, study day will be defined as (Date of assessment – date of first administration of IP) +1. Using this definition, the day of first dose of IP will be Day 1 and the scheduled visit date of Week 4 will be study day 29 (=28+1) for example.

If multiple readings are recorded within a single visit window, the following rules will be followed.

- If there are two or more observations within the same visit window, then the non-missing one closest to the scheduled visit will be used in the analysis.
- If two observations are equidistant from the scheduled visit, then the non-missing observation with the earlier collection date will be used in the analysis.
- If two observations are collected on the same day, then the non-missing one with the earlier collection time will be included in the analysis.

[figure not shown]
If a visit window does not contain any observations, then the data will remain missing.

For overall analyses not based on any particular study visit, all data will be listed and/or analysed, including any repeat or unscheduled visits, unless otherwise specified.

